12.7. Appendix 7: Reporting Standards for Missing Data

12.7.1. Premature Withdrawals

Element	Reporting Detail
General	
 Participant study completion (i.e. as specified in the protocol) was defined as completing all phases of the study including the follow-up visit. Withdrawn participants may be replaced in the study. All available data from participants who were withdrawn from the study will be listed and all available planned data will be included in summary tables and figures, unless otherwise specified. Withdrawal visits will be slotted as per Appendix 3: Assessment Windows or will be summarised as withdrawal visits.

12.7.2. Handling of Missing Data

Element	Reporting Detail
General	
 Missing data occurs when any requested data is not provided, leading to blank fields on the collection instrument: 
 These data will be indicated by the use of a “blank” in participant listing displays. Unless all data for a specific visit are missing in which case the data is excluded from the table. Answers such as “Not applicable” and “Not evaluable” are not considered to be missing data and should be displayed as such.
Outliers	
 Any participants excluded from the summaries and/or statistical analyses will be documented along with the reason for exclusion in the clinical study report.
BAL Pharmacodynamic endpoints	
 No missing data will be imputed.
Blood Pharmacodynamic endpoints	
 Responses unquantifiable due to being below LLQ will be imputed as ½ LLQ. Responses above ULQ will be imputed as ULQ.

12.7.2.1. Handling of Missing and Partial Dates

Element	Reporting Detail
General	
 Partial dates will be displayed as captured in participant listing displays.
Concomitant Medications/ Medical History	
 Partial dates for any concomitant medications recorded in the CRF will be imputed using the following convention: 
 If the partial date is a start date, a '01' will be used for the day and 'Jan' will be used for the month If the partial date is a stop date, a '28/29/30/31' will be used for the day (dependent on the month and year) and 'Dec' will be used for the month. The recorded partial date will be displayed in listings.

12.7.2.2. Handling of Missing Data for Statistical Analysis

For BAL endpoints, any participant that has missing data for baseline (2h) or 26h (LPS lobe) does not meet the criteria to be included in the evaluable population and therefore will be excluded from the analysis. No imputation will be performed.

For analyses of repeated measures data (blood biomarkers), responses that are unquantifiable due to being below LLQ will be imputed as $\frac{1}{2}$ LLQ and above ULQ will be imputed as ULQ, whilst for any other missing data SAS PROC MCMC automatically assumes/implements a missing at random/multiple imputation approach if any of the supplied response variables are missing. Given this is a proof of mechanism study, this is deemed sufficient.

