Theoretical risk: Potential suicidal ideation	GSK2798745 is considered to be a CNS-active drug. There has been some concern that some CNS-active drugs may be associated with an increased risk of suicidal thinking or behaviour when given to some patients with certain conditions. GSK considers it important to monitor for such events before or during clinical studies with CNS-active compounds. Participants being treated with GSK2798745 should be assessed at screening for suicidality.	Participant Selection: The risk of such an event would be very low in single-day dose trials in healthy volunteers; however, participants who, in the investigator/designee's judgement, poses a significant suicide risk, will be excluded from the study. A C-SSRS questionnaire will be completed before and after dosing.
Study procedures-related		
Risk of adverse events following delivery of LPS	Previously reported segmental LPS related adverse events include pleuritic pain, pyrexia, head ache, nausea and alveolitis [Hohlfeld, 2008; Holz, 2015]. It is known that LPS and pro-inflammatory mediators can cause gut permeability [Al-Sadi, 2014; Guo, 2013]. We expect the systemic exposure to LPS and systemic inflammatory response to LPS to be minimal following the segmental topical dose of 4ng/kg LPS. As such, we assess the risk to increased gut permeability, and potential increased bioavailability, with this regimen to be low.	Participant Monitoring: Participants will be monitored with safety assessments, including clinical laboratory tests, physical examination, ECGs, vital signs (including temperature), pulse oximetry and spirometry during the study. Experienced site staff will conduct the procedures. Participants will be carefully monitored and managed with standard procedures in the event of complications.
Risks associated with bronchoscopy and BAL sampling:	Procedure related complications include cough, transient fever, chills and myalgias, transient infiltrates, bronchospasm, transient fall of lung function, transient decrease in baseline PaO2 (partial pressure of oxygen in arterial blood).	

Potential Risk of Clinical Significance	Summary of Data/Rationale for Risk	Mitigation Strategy
Risk associated with blood draws	Fainting, mild pain, bruising, irritation or redness.	Experienced site staff will follow standard approaches for managing events related to blood draws.

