7.3. Exploratory Pharmacodynamic and Biomarker Analyses

7.3.1. Endpoint / Variables

Table 3 gives the matrices and sampling schemes for each of the exploratory biomarker endpoints.

Table 3 Exploratory Biomarkers and Corresponding Sampling Schemes

Matrix	Endpoint / Analyte	Sampling Scheme
BAL	Albumin SP-D vWF IL-6 IL-8 TNF-alpha MPO Urea White blood cell counts and differentials (except neutrophils)	2h, 26h
Blood	Total protein (plasma) Albumin (plasma) SP-D (serum) vWF (serum) IL-6 (serum) IL-8 (serum) TNF-alpha (serum) Immature SP-B (serum) urea (plasma) CRP (serum)	2h, 3h, 8h, 26h

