7.3.5.1. Blood biomarkers

The following text is the general method for analysing and reporting blood biomarkers that follow the sampling scheme in [Table 3](#).

Endpoint / Variables							

 Each blood biomarker and the sampling timepoints are listed in Table 3. It is anticipated that biomarkers will require log-transformation in all analyses to improve model fitting. Following model fitting, back-transformation will occur and treatment comparisons at each of the sampling timepoints will be expressed as a percentage change for GSK2798745 relative to placebo. 							
Model Specification							

 Each blood biomarker will be analysed using a repeated measures mixed model (MMRM) fitted in a Bayesian framework with all covariates having non-informative priors using PROC MCMC in SAS or other software. **analyte** in the text below should be replaced by the specific blood biomarker in the analysis. The terms to be fitted in the model: 							

  
 Type	Name	
   
 Dependent variable	 
 **analyte** response 	
 
 Fixed categorical independent variables	 
 Treatment Sampling timepoint Sampling timepoint interacted with treatment 	
  
		Type	Name	Dependent variable	
 **analyte** response 	Fixed categorical independent variables	
 Treatment Sampling timepoint Sampling timepoint interacted with treatment
Type	Name						
Dependent variable	
 **analyte** response 						
Fixed categorical independent variables	
 Treatment Sampling timepoint Sampling timepoint interacted with treatment 						
Information on the effects and prior distributions for parameters:							

Type	Name (#Levels)	Parameters	Priors
Fixed Categorical	Intercept (1)	#1 Intercept	N(Mean= 0, Var=1E6)
	Treatment (2)	#1 Placebo	N/a (constraint=0)
		#2 GSK2798745	N(Mean=0, Var=1E6)
	Sampling Timepoint (4)	#1 2h	N/a (constraint=0)
		#2 3h	N(Mean=0, Var=1E6)
		#3 8h	N(Mean=0, Var=1E6)
		#4 26h	N(Mean=0, Var=1E6)
	Treatment*Sampling Timepoint (8)	#1 Placebo*2h	N/a (constraint=0)
		#2 Placebo*3h	N/a (constraint=0)
		#3 Placebo*8h	N/a (constraint=0)
		#4 Placebo*26h	N/a (constraint=0)
		#5 GSK2798745*2h	N/a (constraint=0)

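### Modelling half-LLQ substitutes for exploratory blood biomarkers as observed values can distort the treatment ratio and its 95% interval when there is a real effect and enough values are censored

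*SAP*

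**What the plan says.** SAP section 12.7.2 gives the rule for blood pharmacodynamic endpoints: "Responses unquantifiable due to being below LLQ will be imputed as" half the LLQ, and "Responses above ULQ will be imputed as ULQ". Section 12.7.2.2 repeats it for the repeated-measures analysis: "responses that are unquantifiable due to being below LLQ will be imputed as" half the LLQ. It separates these values from true gaps: "whilst for any other missing data SAS PROC MCMC automatically assumes/implements a missing at random/multiple imputation approach". The stated reason is short: "Given this is a proof of mechanism study, this is deemed sufficient".

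The model is in SAP section 7.3.5.1: "Each blood biomarker will be analysed using a repeated measures mixed model (MMRM) fitted in a Bayesian framework". Its terms are treatment, time point and their interaction, with N(0, 1E6) priors on the fixed effects. Log transformation is anticipated, and results are back-transformed to a percentage change at 2, 3, 8 and 26 h. Each time point gets a 95% credible interval and the posterior probability statements of SAP Table 2.

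SAP Table 3 lists ten blood analytes, including serum IL-6, IL-8 and TNF-alpha. Protocol section 3.3.1 says of the challenge: "We expect the systemic exposure to LPS and systemic inflammatory response to LPS to be minimal".

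There is no censored likelihood, no limit on the BLQ fraction and no sensitivity analysis for the substitution.

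**The concern.** A BLQ value tells us only that the response lies below a known limit. Replacing it by one constant, the same in both arms, does three things on the log scale. It removes the spread of the censored values. It erases any difference between arms among them. It also places them ln 2 = 0.69 below the log limit, a distance fixed by convention rather than by the data.

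The estimate and its interval then depend partly on where the assay limit happens to fall. The direction is not fixed. Heavy censoring pulls the ratio towards 1. Light censoring with a small SD pushes it away from 1, because half the LLQ is then far below where the censored values really lie.

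At stake is the reading of the exploratory blood markers of barrier injury and inflammation. Participants are healthy and one lung segment is challenged, so some serum cytokine values below the limit are foreseeable, though the documents do not say how many.

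**Working it through.** **Inputs from the documents.** 30 per arm, 1:1 (Protocol 10.1). The only log-scale variance given is 0.25 for BAL total protein, 95% CI 0.13 to 0.69 (Protocol 10.1), so SD 0.5. The planned effect for BAL protein is a 30% reduction, ratio 0.7.

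**Assumed for blood markers.** Log SD 0.3 to 1.0, true ratio 0.5 to 1.0, and 10% to 90% of placebo values BLQ. None of these is stated for blood.

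**The plan's own figures first.** The plan states no bias, coverage or BLQ figure for blood. As a check on scale, its minimum effect for success on BAL protein is 19%: 1 − exp(−1.645 × 0.5 × √(2/30)) = 19.1%. Its 82% probability of success is also recovered (81.6%) by averaging one-sided 5% power over a variance distribution matched to the stated interval.

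**Bias.** Take the placebo log mean as 0 and let p be the placebo BLQ fraction.
- Log limit L = SD × z(p); substituted value c = L − ln 2.
- For an arm with mean μ, BLQ fraction P = Φ((L − μ)/SD).
- Mean after substitution = P·c + μ(1 − P) + SD·φ((L − μ)/SD).
- Expected ratio = exp(active mean − placebo mean).

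Example with SD 0.5, ratio 0.7, p = 0.80:
- L = 0.5 × 0.8416 = 0.4208; c = 0.4208 − 0.6931 = −0.2723.
- Placebo: 0.80 × (−0.2723) + 0.5 × 0.2800 = −0.0779.
- Active: μ = ln 0.7 = −0.3567, (L − μ)/SD = 1.555, P = 0.940; mean = 0.940 × (−0.2723) − 0.3567 × 0.060 + 0.5 × 0.1191 = −0.2179.
- Ratio = exp(−0.2179 + 0.0779) = 0.87, against a true 0.70.

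**Coverage.** This is the share of simulated trials in which the 95% t interval for the log ratio (58 df) contains the true value. With complete data, no baseline covariate and vague priors, that interval approximates the planned contrast at one time point. True ratio 0.7, 40,000 trials per row:

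| Log SD | Placebo BLQ | Active BLQ | Expected ratio | Coverage |
|---|---|---|---|---|
| 0.3 | 10% | 46% | 0.60 | 72% |
| 0.3 | 30% | 75% | 0.62 | 80% |
| 0.3 | 50% | 88% | 0.69 | 95% |
| 0.3 | 80% | 98% | 0.86 | 21% |
| 0.5 | 30% | 57% | 0.68 | 94% |
| 0.5 | 50% | 76% | 0.73 | 94% |
| 0.5 | 70% | 89% | 0.82 | 67% |
| 0.5 | 80% | 94% | 0.87 | 30% |
| 1.0 | 30% | 43% | 0.73 | 95% |
| 1.0 | 50% | 64% | 0.78 | 92% |
| 1.0 | 80% | 88% | 0.89 | 48% |

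Separate runs differ by a point or two, so the 80% rows are quoted as about 20% to 49%, and 70% BLQ at SD 0.5 as 67% to 69%. Allowing unequal variances changes little (68% at 70% BLQ, 30% at 80%).

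**Other true ratios, SD 0.5.**
- Ratio 1: estimate 1.00 and coverage 95% at every fraction tried.
- Ratio 0.9: coverage at least about 91% up to 80% BLQ.
- Ratio 0.8: 0.87 with 89% at 70% BLQ; 0.90 with 71% at 80%.
- Ratio 0.5: 0.63 with 53% at 50% BLQ; 0.76 with 2% at 70%.
- Coverage first drops below 50% at about 76% placebo BLQ for ratio 0.7 and about 51% for ratio 0.5.

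**Censored likelihood, SD 0.5, 400 trials per cell.** At ratio 0.7, coverage is 94%, 96%, 94% and 90% at 30%, 50%, 70% and 80% BLQ, with median estimates of 0.70 to 0.72. At ratio 0.5 the median estimate falls to 0.44 at 70% BLQ and 0.16 at 80%, where the active arm is 97% to 99% BLQ.

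**Limit of that remedy.** At ratio 0.7 and 80% placebo BLQ, the chance that all 30 active values are BLQ is 0.979^30 = 53% at SD 0.3 and 0.940^30 = 16% at SD 0.5. The data then put no lower bound on the active mean, and the vague priors add almost none.

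**The case against.** The strongest reply is that the harm needs a real effect and, for the worst coverage, heavy censoring, and the documents establish neither. That stands. A reader might infer from the protocol's expectation of a minimal systemic response that most cytokine values will be BLQ. But that sentence concerns safety and bioavailability, not assay detectability, and it cuts both ways: little systemic response also makes a true ratio near 1 more likely, where the distortion is small.

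A reader might also infer that blood ratios are biased in general, or that their intervals usually miss the truth. The results with no true difference, and those at ratio 0.7, SD 0.5 and 30% to 50% BLQ, do not support this. Nor is it shown that a real fall would be reported as no effect with high certainty: the 80% BLQ rows still report an 11% to 14% fall, and no posterior probability was computed.

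The check is a t interval at one time point, not the four-time-point Bayesian model. That is a fair limit on precision, but the planned likelihood treats the constants in the same way.

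The SAP has some safeguards. LLQ and ULQ lines are to be drawn on figures where appropriate, participant profiles are planned for each blood marker (Figure 2.27), and residual plots are an optional model check. These would reveal heavy censoring, but they would not change the reported ratio or interval.

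Finally, these endpoints are exploratory. That limits the consequence but does not make the substitution accurate.

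**Conclusion.** The point holds conditionally. The substitution rule is in force and can give a wrong ratio and an interval with poor coverage when there is a true effect. It attenuates the effect under heavy censoring and exaggerates it when the SD is small and censoring is light to moderate. Because the blood BLQ fraction, SD and effect are unknown, the size is a range over assumptions and not a prediction for any marker.

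No decision rule depends on it: the substitution is stated for blood only, and the interim and success criteria use BAL total protein. A reader might also infer that a censored likelihood cures the problem in every setting. It does not when an arm is almost entirely BLQ, so it needs a stopping point. It is worth correcting before analysis because the remedy is cheap and the SAP currently sets no limit.

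**What to change.** Amend SAP sections 12.7.2, 12.7.2.2 and 7.3.5.1 as follows.

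1. In the PROC MCMC blood-biomarker model, treat values below the LLQ as left-censored, with likelihood term Φ((log LLQ − μ)/σ), and values above the ULQ as right-censored, with the upper-tail term. Within the repeated-measures structure this can be done by sampling censored values as unknowns bounded by the limit. Keep half-LLQ for descriptive summaries and plots only.
2. Report the number and percentage censored by arm and time point for each marker.
3. Pre-specify a numerical ceiling on the censored fraction, or a minimum number of quantifiable values per arm and time point. Beyond it, model no ratio and report only the proportion detectable.

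The cost is SAP wording and a little extra programming in code already planned in PROC MCMC. Intervals will be wider where censoring is heavy, and some marker and time-point combinations will have no ratio.

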12.8. Appendix 8: Values of Potential Clinical Importance

12.8.1. Laboratory Values

Hematology			
Analyte	Effect	Relative – Low (Multipliers of LLN)	Relative – High (Multipliers of ULN)
White Blood Cell Count (x10 ⁹ /L)		0.67	1.82
Neutrophil Count (x10 ⁹ /L)		0.83	
Hemoglobin (g/L)	Male		1.03
	Female		1.13
Hematocrit (ratio of 1)	Male		1.02
	Female		1.17
Platelet Count (x10 ⁹ /L)		0.67	1.57
Lymphocytes (x10 ⁹ /L)		0.81	
Monocytes (x10 ⁹ /L)		0.5	1.8
Red Blood Cell Count (x10 ⁹ /L)		0.7	1.7
Reticulocytes (%)		0	1.5

Chemistry			
Analyte	Effect	Relative – Low (Multipliers of LLN)	Relative – High (Multipliers of ULN)
Calcium (mmol/L)		0.91	1.06
Glucose (mmol/L)		0.71	1.41
Potassium (mmol/L)		0.86	1.10
Sodium (mmol/L)		0.96	1.03
Blood Urea Nitrogen (mmol/L)		0.7	1.5
Total Protein (mg/dL)		0.6	1.7
Creatinine phosphokinase (IU/L)		0	1.8
Direct Bilirubin (umol/L)		0	1.6
Analyte	Effect	Relative – Low (Absolute Value)	Relative – High (Absolute Value)
Creatinine (umol/L)	Chg from Baseline		> 44 umol/L

Urinalysis:

During the study, a dipstick result (positive or negative) will be recorded for each participant at each timepoint. If the dipstick result is positive, a microscopy will be performed. The urinalysis dipstick result at day 8 and day 2 will be compared with day -

1 (pre-dose) and data of PCI will be flagged where a result changes from negative to positive and/or a microscopy is performed.

Faecal Occult Blood Test:

FOBT is performed at screening and follow-up with measurement as haemoglobin (iFOBT) ng/ml. Any positive haemoglobin measurement (≥ 50 ng/ml) will be flagged as potentially clinically important and all results for a participant with at least one flagged result will appear in listings.

Liver Function			
Test Analyte	Units	Category	Clinical Concern Range
ALT/SGPT	U/L	High	$\geq 2x$ ULN
AST/SGOT	U/L	High	$\geq 2x$ ULN
AlkPhos	U/L	High	$\geq 2x$ ULN
T Bilirubin	$\mu\text{mol/L}$	High	$\geq 1.5x$ ULN
T. Bilirubin + ALT	$\mu\text{mol/L}$, U/L	High	$\geq 1.5x$ ULN T.Bilirubin + $\geq 2x$ ULN ALT

Other				
Laboratory Parameter	Units	Category	Clinical Concern Range	
			Low Flag (< x)	High Flag (>x)
Cardiac Troponin (cTn)	ng/ml			>ULN or 2x Baseline Value
Coagulation Profile				
International Normalisation Ratio (INR)			< 0.85	> 1.15
Prothrombin Time (PTT)	%		< 70	> 120
Fibrogen	g/l		< 1.7	> 4.2

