Myocardial toxicity	Dogs (4-week study): at 30 mg/kg/day, myofibre degeneration/necrosis and inflammation (2 animals)	
Participant Selection: Participants with any history or current disease constituting a risk when taking the study treatment, including relevant history of acute coronary syndromes (including unstable angina), coronary angioplasty, or stenting, will be excluded.
 
Participant Monitoring: Cardiac troponin levels will be monitored and ECGs will be done during the study.
 
Participant Exposure: Exposure levels will be maintained below the threshold detailed in the Dose Justification Section (see Section 5.5).

Potential Risk of Clinical Significance	Summary of Data/Rationale for Risk	Mitigation Strategy
Mortality/moribund condition; poor viability	
Dogs (4-week study): at 30 mg/kg/day, one male terminated early (Day 6) due to poor clinical condition. Another male had transient whole body shaking on Days 8 and 9.
 
Dogs (13-week study): at 10 mg/kg/day one male was terminated early (Day 74) due to welfare reasons.
 
Rats (micronucleus and comet study): mortality occurred following 1 to 3 doses at <math>\geq 600</math>mg/kg/day
	
Participant Monitoring: Weight and adverse events reported by participants will be monitored.

Gastrointestinal (GI) and/or hepatic toxicity	
GI toxicity: <math>\geq 3</math> mg/kg/day in dogs and at 30 and 300 mg/kg/day in rats, consisting of mucosal erosion/ulceration in the stomach and/or duodenum.
 
Hepatic Toxicity: Biliary epithelial hypertrophy/hyperplasia and periductal mixed inflammatory cell infiltrate into the liver was observed at 300 mg/kg/day in rat (7-day study) and focal hepatocellular degeneration in 1 male dog at 30 mg/kg/day (4-week study)
	
Participant Selection: Participants with active ulcer disease or GI bleeding or those who are taking concomitant medications, including nonsteroidal anti-inflammatory drugs (NSAIDs) and steroids, will be excluded. Assessment of faecal occult blood will be performed before and after dosing.
 
Participant Monitoring: Participants will be monitored for GI intolerance (e.g by adverse events such as abdominal discomfort) and sequential clinical chemistry analysis, including liver enzymes. Follow-up faecal occult blood test (FOBT) will be conducted.

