### 9.7.7. Faecal Occult Blood Test (FOBT)

Based on the preclinical finding of gastric erosions, FOBT will be performed before and after dosing (See [Section 2](#)). Details on FOBT are provided in the SRM.

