23.	All Subjects	LB5	Listing of All Laboratory Data for Participants with Any Value of Potential Clinical Importance	ICH E3	SAC [1]
24.	All Subjects	LB5	Listing of Laboratory Values of Potential Clinical Importance		SAC [1]

ICH: Listings					
No.	Population	IDSL / Example Shell	Title	Programming Notes	Deliverable [Priority]
25.	All Subjects	LB14	Listing of Laboratory Data with Character Results	ICH E3	SAC [1]
26.	All Subjects	UR2A	Listing of Urinalysis Data for Participants with Any Value of Potential Clinical Importance	ICH E3	SAC [1]
ECG					
27.	All Subjects	EG3	Listing of All ECG Values for Participants with Any Value of Potential Clinical Importance	IDSL	SAC [1]
28.	All Subjects	EG3	Listing of ECG Values of Potential Clinical Importance	IDSL	SAC [1]
29.	All Subjects	EG5	Listing of All ECG Findings for Participants with an Abnormal ECG Finding	IDSL	SAC [1]
30.	All Subjects	EG5	Listing of Abnormal ECG Findings	IDSL	SAC [1]
Vital Signs					
31.	All Subjects	VS4	Listing of All Vital Signs Data for Participants with Any Value of Potential Clinical Importance	IDSL	SAC [1]
32.	All Subjects	VS4	Listing of Vital Signs of Potential Clinical Importance	IDSL	SAC [1]

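### Haemoglobin and haematocrit have no low-side flag in SAP 12.8.1, so a fall in either does not by itself trigger laboratory Listings 23 or 24

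*SAP*

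**What the plan says.** SAP 12.8.1 sets limits of potential clinical importance as multiples of LLN (low) and ULN (high). The rows "Hemoglobin (g/L" and "Hematocrit (ratio of 1" are split by sex, and each has an upper multiplier and an empty low cell. The row "Red Blood Cell Count" has both limits, 0.7 × LLN and 1.7 × ULN. Creatinine is the only laboratory analyte in the chemistry and haematology tables with a change-from-baseline rule.

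The same section gives FOBT its own rule: a positive result (at or above 50 ng/ml) "will be flagged as potentially clinically important and all results for a participant with at least one flagged result will appear in listings".

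In SAP 12.11.11, Listing 23 is the "Listing of All Laboratory Data for Participants with Any Value of Potential Clinical Importance", and Listing 24 prints the flagged values themselves. Table 3.6 (SAP 12.11.7) summarises haematology change from baseline by group. No listing prints haematology results for every participant.

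Protocol 3.3.1 describes the gastrointestinal findings in dogs and rats as "consisting of mucosal erosion/ulceration in the stomach and/or duodenum". Protocol 9.7.7 links the stool test to them: "Based on the preclinical finding of gastric erosions, FOBT will be performed before and after dosing".

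**The concern.** Blood loss lowers haemoglobin and haematocrit. The plan collects both on Day -1, at 30 h on Day 2 and at follow-up, but its flags for these two analytes respond only to a rise. For a drug with a named risk of erosion or ulceration in the stomach and duodenum, the rule looks the wrong way.

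At stake is the individual-level safety record. The flag-driven listings are the part of the laboratory report that applies a fixed rule and does not depend on anyone's judgement. If a fall in the two most direct measures of blood loss cannot enter them, a participant with a moderate fall may be visible only inside a group summary.

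**Working it through.** There is no sample size, power or error-rate figure to reproduce. The check is a reading of the flag table, a trace from flags to displays, and one piece of arithmetic.

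**1. Limits in SAP 12.8.1**

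| Analyte | Low (× LLN) | High (× ULN) |
|---|---|---|
| Haemoglobin, male / female | blank / blank | 1.03 / 1.13 |
| Haematocrit, male / female | blank / blank | 1.02 / 1.17 |
| Red cell count | 0.7 | 1.7 |
| Platelets | 0.67 | 1.57 |
| Neutrophils | 0.83 | blank |
| Lymphocytes | 0.81 | blank |
| Reticulocytes | 0 | 1.5 |
| Blood urea nitrogen | 0.7 | 1.5 |

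**2. Are the blanks real?** They appear to be. Neutrophils and lymphocytes keep a low value with an empty high cell, and platelets and red cells keep both, so column position survived in this table. The haemoglobin and haematocrit values also make no sense as low limits: 1.02 to 1.17 times LLN lies above LLN and would flag values inside the reference range.

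**3. From flags to displays.** A low haemoglobin or haematocrit meets no criterion in 12.8.1, so it triggers neither Listing 23 nor Listing 24. The remaining routes are:

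- *FOBT.* A positive result is flagged, and Listing 49 prints abnormal results. FOBT is done at screening and at follow-up. The post-dose cards are handed out at discharge and returned by the Day 8 visit (Protocol 2.3).
- *Other laboratory flags.* Red cells below 0.7 × LLN, "Blood Urea Nitrogen (mmol/L" above 1.5 × ULN, or reticulocytes above 1.5 × ULN. Any one brings the participant's whole laboratory record, haemoglobin included, into Listing 23.
- *Adverse events.* Protocol 9.7.6 has the investigator review each laboratory report and record clinically relevant changes as adverse events, which reach Listing 13.

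**4. Strength of the red cell route.** This is the only low-side red-cell flag. Let k be the baseline red cell count divided by LLN. The fall needed to reach the limit is 1 − 0.7/k. The documents do not give k, so a range of 1.0 to 1.3 is assumed.

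| k (assumed) | Calculation | Fall needed |
|---|---|---|
| 1.0 | 1 − 0.7/1.0 | 30.0% |
| 1.1 | 1 − 0.7/1.1 | 36.4% |
| 1.2 | 1 − 0.7/1.2 | 41.7% |
| 1.3 | 1 − 0.7/1.3 | 46.2% |

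If haemoglobin falls in proportion to the red cell count, a fall of less than about 30% to 46%, depending on baseline, trips no low-side red-cell flag.

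**5. What is left uncovered.** A moderate fall on Day 2, with the follow-up FOBT negative or missing, no other analyte flagged and no adverse event recorded, appears in no participant-level display.

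**The case against.** The strongest reply is that the plan already monitors this hazard by the means the protocol chose. Protocol 3.3.1 names erosion and ulceration in animals, reports no risk identified in clinical studies, and lists FOBT, adverse events and sequential chemistry as the monitoring; haematology is not on that list. The SAP displays all of these. A positive screening FOBT is an exclusion, and dosing lasts one day. The post-dose cards cover the days after discharge, and the investigator must review every laboratory report whatever the flags say. Most of this stands, and it is why the point is minor.

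It also rules out two stronger readings that a reader might be tempted by.

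- *That a participant who bled would appear in no laboratory listing.* The documents do not support this. A positive FOBT is flagged and listed, and a red cell, urea nitrogen or reticulocyte flag brings the full record into Listing 23.
- *That even a very large fall, say 50 g/L, would trigger no listing.* This cannot be asserted. With a proportional fall in red cells, the red cell flag is reached if k is below 0.7/(1 − 50/b), where b is baseline haemoglobin. For an assumed b of 160 g/L this is 0.7 × 160/110 = 1.02; for 130 g/L it is 0.7 × 130/80 = 1.14. The flag may or may not fire. Nor can one say that Table 3.6 would hide such a fall, because its standard shell is not in the documents and may show minimum values.

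The reply does not close the gap. FOBT gives no result at the time of the Day 2 blood draw and depends on a returned card. The red cell limit is far down. Urea nitrogen and reticulocyte flags are incidental. Adverse event recording rests on judgement, which a fixed flag is meant to complement.

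**Conclusion.** The point holds as a minor reporting gap. Haemoglobin and haematocrit are flagged only when high, so a fall in either does not by itself reach Listings 23 or 24. The cases affected are moderate falls with a negative or missing follow-up FOBT, no other flagged value and no adverse event. The documents give no basis for estimating how many participants that would be.

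The 30% to 46% figure rests on an assumed baseline red cell count of 1.0 to 1.3 × LLN, and applying it to haemoglobin assumes the two fall in proportion. The finding that no low-side rule exists rests on neither assumption. No endpoint, interim decision or participant-level action is affected.

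**What to change.** In SAP 12.8.1, add a low-side entry for haemoglobin and haematocrit, either as a multiple of LLN or as a decrease from the Day -1 value, which SAP 5.2 already defines as the laboratory baseline. The creatinine row is a precedent for the second form. The sponsor's safety physician should set the threshold; this review proposes none. Listings 23 and 24 then pick up the new flag without further change. If the blank is deliberate, the SAP should say so and give the reason.

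The cost is one table entry for each analyte and one programming condition. No new data, visit or display is needed, and participant management is unchanged.
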